4.1. General Principles

Descriptive statistics (mean, standard deviation, median, range, etc.) will be used to summarize continuous variables, and counts and proportions will be used to summarize categorical variables by treatment group. For time-to-event variables, Kaplan-Meier method will be used to estimate the survival function and estimate the median survival time and its 95% confidence interval, and survival curves will be provided.

Unless otherwise specified, the cycle baseline measurement for Cycle 1 is defined as the last available valid measurement within 7 days before the start of study medication on Cycle 1 Day 1; the baseline measurement for subsequent cycles is defined as the last available valid measurement within 3 days before the start of study medication on Cycle 1 Day 1. Unless otherwise specified, study baseline measurements are defined as the last available valid measurement prior to the first dose of study drug. If the last valid measurement coincides with the start date of the first study drug administration, the measurement will be considered as baseline measurement. Adverse events or concomitant medications that occurred on the day of the first dose of study drug are considered postbaseline.

The start date of each cycle is defined as the first day of the cycle, i.e., the date of the first study drug administration of the cycle; the end date of each cycle is defined as the start date of the next cycle, or the first day of the cycle +36 days if the next cycle is not entered.

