4.4.2.1. Incidence of serious neutropenia events

The total number of SN events is the total number of cycles with at least one ANC value $< 0.5 \times 10^{9}$ /L. For example, two ANC values less than 0.5 x 10⁹/L during Cycle 2 are counted as only one SN event. If a patient does not experience any SN events, the number of SN events for that patient will be counted as zero. Unscheduled data will be included and and actual SN assessment date (non-visit date) will be used. Whether a patient experienced a SN event is a binary variable (yes or no); 'yes' if ≥ 1 cycles with a SN event is observed; and 'no' otherwise.

SN events will be summarized by treatment group using descriptive statistics. Part 2 of the study will analyze the adjusted rate ratio (aRR) between the two treatment groups based on a modified Poisson regression model. The model includes baseline ANC measurement as covariate and IRT-based randomization stratification factors including number of lines of therapy (1st line versus 2nd/3rd line), ECOG (lines 0-1 versus 2) (not included in the actual analysis), and brain metastases (yes versus no), as well as treatment arm as fixed effects. Logarithmic transformed values of the number of cycles will be included in the modeling as offset variables. P-values, aRR (Trilaciclib versus placebo) and their 95% CIs will be provided for the 2-sided tests. In addition, Cochran-Mantel-Haenszel (CMH) weights will be used to calculate the adjusted rate difference between the two arms (Trilaciclib versus placebo) and its 95% CI in Part 2 of the study, and stratified exact CMH method will be used to calculate P values under the 2-sided test according to IRT-based randomization stratification factors to test the stability of the analysis results.

4.4.2.2. Incidence of red blood cell transfusion events occured on/after Week 5

Each red blood cell (RBC) transfusion (including whole blood transfusion and each red blood cell component) occured on/after Week 5 is defined as a separate event and included in the efficacy analysis. Whether a patient experiences a RBC transfusion event is defined as a binary variable (yes or no); "yes" if a total number of RBC transfusion events ≥ 1 is observed, otherwise "no".

The statistical analysis method is similar to that described for SN incidence in Section 4.4.2.1, except hemoglobin (HGB) baseline measurement will be used as covariate instead of

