ANC baseline measurement in a modified Poisson regression model. In addition, the offset variables will be log-transformed values for duration of treatment (weeks) rather than cycles.

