4.4.2.4. Total occurrence of major adverse hematologic event

Major adverse hematologic event (MAHEs) are composite endpoints to assess the effect of Trilaciclib. MAHE consists of the following 5 component events:

- Involved hospitalization
- Leading to chemotherapy dose reduction
- Febrile neutropenia
- Extended SN (greater than 5 days)
- RBC transfusion occured on/after Week 5.

The total number of events for each MAHE component is the sum of the number of events that occurred on the date of first study drug administration and before the end of the last treatment cycle. The total number of events for MAHEs during treatment is the sum of the number of events for each MAHE component. For patients who does not experience any MAHE, the total number of MAHE events is 0.

MAHEs will be coded using the most current version of MedDRA and the total number of MAHEs, duration of treatment (weeks), weekly event rates, and cumulative event rates every 3 weeks will be summarized by number of lines of treatment. According to the actual MAHEs, the above summaries will be repeated separately by component events , but for MAHE component events leading to chemotherapy dose reduction and SN prolongation, the cumulative

event rates will be summarized by cycle rather than every 3 weeks. Part 2 of the study will also analyze the adjusted rate ratio between the Trilaciclib and placebo groups using a negative binomial regression model. The model includes the three IRT-based randomization stratification factors and treatment group as fixed effects, and the log-transformed values of treatment duration (weeks) or cycle number as offset variables. Two-sided P values, aRR (Trilaciclib versus placebo) and their 95% CIs will be provided. Cumulative incidence of MAHEs within specified subgroups will be presented using forest plots.

Time to first onset (months) for each MAHE component event = (date of first MAHE component event – date of first study drug administration + 1)/30.

For patients who developes MAHEs, the time (months) from the first study drug administration (randomization date in Part II) to the first occurrence of MAHEs will be summarized and Kaplan-Meier curves will be provided. Time to first MAHE refers to the event with the shortest time to first occurrence of the MAHE component; if a patient does not have an MAHE, it will be censored at the end date of the last cycle, date of death, end of study, or last contact date for that patient, whichever cames first.

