4.4.3.3. Other dichotomous endpoints

The total number of events below is the total number of cycles with at least one event. If a patient does not experience any of the following events during the treatment period, the number of events for that patient is zero. 'Yes' if ≥ 1 of the following events are observed; otherwise 'No'.

- Incidence of Grade 3 and 4 Hematologic Toxicities: Grade 3 and 4 hematologic toxicities refers to hematology laboratory results with CTCAE Grade 3 or 4.
- Incidence of platelet transfusion (during chemotherapy)
- Incidence of febrile neutropenia

Each of the following events with a unique start date will be defined as a separate event during the treatment period. Yes if the total number of the following events observed is ≥ 1 , otherwise no.

- Incidence of intravenous or oral antibiotics
- Incidence of infectious serious adverse events
- Incidence of serious adverse events of lung infection

Determine if the following medications is used in that cycle by comparing the start and end dates of each use of the following medications with the start and end dates of the treatment cycle. The total number of events with the following medications is the total number of cycles with at least one dose of the following medication. If a patient did not take the following medications during the treatment period, the number of events for that patient is 0.

- Erythropoiesis-stimulating agent (ESA) Usage
- Recombinant human interleukin-11 (IL-11) use rate
- Thrombopoietin (TPO) use

The total number of events as well as the incidence of the above dichotomous variables will be summarized descriptively and tabulated in detail by patient. The statistical analysis approach is similar to that described for SN incidence in Section 4.4.2.1, except that baseline ANC measurements will not be included as covariates in the modified Poisson regression model.

In addition, for comparing the incidence of antibiotic administration, SAEs of infection, and SAEs of lung infection between the Trialciclib and placebo groups, the offset variable in the modified Poisson regression model will be the log transformed duration of treatment (weeks) rather than the number of cycles.

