4.6.1. Extent of Study Drug Exposure

Duration of exposure to study drug during the treatment period and number of treatment cycles started will be summarized using descriptive statistics. Cumulative actual dose, cumulative planned dose for compliance, cumulative planned dose for compliance, medication compliance, and relative dose intensity will be summarized for the different study drugs (Trilaciclib or chemotherapy drugs), respectively.

- Duration of chemotherapy exposure (days) = date of first dose of study drug in last cycle date of first dose of study drug + 21 days
- Number of treatment cycles

A treatment cycle is considered to be started if the subject receives at least one dose of study drug (Trilaciclib/placebo or chemotherapy). Descriptive statistics will be used to summarize the number of cycles started and to summarize the counts and percentages of subjects by the number of cycles started.

Relative dose intensity (%) = (cumulative actual dose administered/cumulative planned dose administered) 100%,

If applicable, the proportion of subjects with dose reductions will be summarized separately by study drug. Number of events with dose reductions will be described and the number and percentage of subjects will be summarized by number of dose reductions.

- The dose of Trilaciclib/placebo will not be adjusted in this trial and will remain at 240 mg/m² unless safety data in Part 1 suggests that dose adjustment of Trilaciclib/placebo is warranted.
- Carboplatin, etoposide and topology are determined by comparing the actual dose on the

respective dosing pages of the current and previous cycles Dose reductions for ticam are shown in Table 1 for Cycle 2 and Day 1 of subsequent cycles.

Dose Level	Etoposide (mg/m ²)	Carboplatin AUC	Topotecan (mg/m ²)
Dose Level -1	Reduce to 75	Decreased to $AUC = 4$	1
Dose Level -2	Reduce to 50	Decreased to $AUC = 3$	0.8

Table 1 Dose reductions for carboplatin, etoposide and topotecan

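### SAP 4.4.2.2 counts red-cell transfusions only from Week 5 but offsets by all treatment weeks, so Weeks 1–4 enter as exposure in which no event can count

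*SAP*

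**What the plan says.** Red-cell transfusion on or after Week 5 is a key secondary endpoint (SAP 4.4.2).

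- **Events.** Under SAP 4.4.2.2 each transfusion that "occured on/after Week 5 is defined as a separate event and included in the efficacy analysis". A yes/no variable per patient is defined as well.
- **Model.** The method is that of the severe neutropenia analysis in 4.4.2.1, with baseline hemoglobin in place of baseline ANC, and "the offset variables will be log-transformed values for duration of treatment (weeks) rather than cycles". No sentence says whether the count or the yes/no variable is the response.
- **Offset-free comparison.** 4.4.2.1 also plans a CMH-weighted rate difference and a stratified exact CMH p-value. These carry over to 4.4.2.2.
- **Treatment duration.** The only formula is in 4.6.1, for the exposure summary: "Duration of chemotherapy exposure (days) = date of first dose of study drug in last cycle", counted from the first dose, plus 21 days. It starts at first dose, not at Week 5.
- **End dates elsewhere.** SAP 4.1 ends a last cycle at "the first day of the cycle +36 days if the next cycle is not entered". For the MAHE components, 4.4.2.4 counts events that "occurred on the date of first study drug administration and before the end of the last treatment cycle". The protocol synopsis, repeated in SAP Appendix 1, limits endpoints to the chemotherapy period unless otherwise specified. No end date is given for the 4.4.2.2 model itself.
- **Weekly rates.** 4.4.2.4 summarises weekly MAHE rates, and "the above summaries will be repeated separately by component events", which includes the transfusion component.

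**The concern.** A log-link Poisson model with an offset estimates events divided by offset time. Here the numerator opens at Week 5 and the denominator at first dose. The first four weeks are a fixed amount of dead time, so they take a larger share of a short treatment than of a long one. If one arm is treated longer, a smaller share of its denominator is dead time and its modelled rate rises relative to the other arm, even with identical true weekly rates from Week 5.

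At stake is the adjusted rate ratio, with its interval and p-value, for a key secondary endpoint. Separately, a weekly rate per arm on this denominator is too low to be read as a rate from Week 5, even when the arms are treated equally long.

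**Working it through.** **The plan's own figures.** The documents give none for this model. The sample-size figure reproduces: simulated Wilcoxon power with 35 per group is 94.5% without and 94.9% with continuity correction, against about 95% stated, and 70/(1 − 0.12) = 79.5, so 80. It does not involve this model.

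**Inputs.** Cycles last 21 days (protocol 5.2) and Week 5 starts 4 weeks after first dose. The earlier median was 4 cycles (protocol 1.3.1, all cancer patients). Length by arm is not given, so I assume mean cycles of 4.2, 4.5 and 5 on trilaciclib against 4 on placebo. I also assume a constant and equal weekly rate from Week 5, a count response and no covariates.

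**Formula.** Expected ratio = [E(weeks from Week 5)/E(offset weeks)] on trilaciclib ÷ the same quantity on placebo.

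For a patient with *c* cycles:

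- Day 1 + 36 end: duration = (21(c − 1) + 36)/7 = 3c + 2.143 weeks; time from Week 5 = 3c − 1.857 weeks.
- 21-day end: duration = 3c weeks; time from Week 5 = max(3c − 4, 0), with mean 3E(c) − 4 + P(c = 1).

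**A. Day 1 + 36 for count and offset**

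| Mean cycles | From Week 5 / offset | Share | Ratio v 4 |
|---|---|---|---|
| 4 | 10.143/14.143 | 0.717 | 1.00 |
| 4.2 | 10.743/14.743 | 0.729 | 1.016 |
| 4.5 | 11.643/15.643 | 0.744 | 1.038 |
| 5 | 13.143/17.143 | 0.767 | 1.069 |

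**B. Day 1 + 36 for the count, 21 days for the offset.** The share at mean 4 is 10.143/12 = 0.845 and at mean 5 is 13.143/15 = 0.876. The ratios are 1.009, 1.020 and 1.037.

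**C. 21 days for both.** Cycles are taken as 1 + Binomial(5, p) or as a beta-binomial with a + b = 1.5. At mean 4, P(c = 1) is 0.010 or 0.127, so the share is 8.010/12 = 0.668 or 8.127/12 = 0.677. At mean 5, P(c = 1) is 0.0003 or 0.039, so the share is 11.000/15 = 0.733 or 11.039/15 = 0.736. The ratios are 1.020–1.023, 1.047–1.054 and 1.087–1.099.

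Overall, the ratio is about 1.01–1.10 when the true ratio is 1, and 1.00 when lengths are equal.

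**Size against noise.** 1,500 trials per scenario were simulated with 40 per arm, 0.031 events per week from Week 5 (the placebo figure in protocol Table 3, used as an assumption), gamma frailty of shape 0.5 and robust errors. The planned offset divided by the aligned offset gave 1.04 at 4.5 v 4 and 1.07 at 5 v 4 under A, and 1.05–1.06 and 1.09–1.10 under C. The standard error of the log ratio was about 0.49–0.57, so a 95% interval spans a factor of about 2.6–3 each way. ln(1.069)/0.52 = 0.13. False positives were 5–7% with either offset. In separate simulations with unequal treatment lengths, an offset starting at Week 5 returned the true ratio for true values of 0.50 and 1.00.

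**Yes/no response.** With the same frailty, the expected ratio at 5 v 4 is 0.965–1.041, on either side of 1.

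**Weekly rate per arm at mean 4 cycles.** The shortfall is 1 − 0.717 = 28% under A and 1 − 0.668 or 1 − 0.677 = 32–33% under C. If the two end dates were mixed as in B it would be 1 − 0.845 = about 15%.

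**The case against.** The strongest reply is that little depends on this. The comparison is distorted only if treatment length differs by arm, and no document gives that. Protocol 1.3.1 reports fewer discontinuations on trilaciclib for adverse events, death and investigator judgment, with one figure (9.0% v 11.0% stopping any study drug for an adverse event). That makes longer trilaciclib treatment plausible but does not establish 5 v 4 cycles. The key secondary endpoints carry no testing hierarchy, and the CMH difference and exact p-value use no offset. All of this stands, and it is why the point is minor. It does not make the offset right, because the event window and the exposure window still disagree by four weeks.

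Three stronger readings are tempting and are not supported:

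- **A reader might infer that the SAP ends the count and the exposure on different dates.** The Day 1 + 36 count comes from the MAHE rule and the 21-day duration from the exposure summary. Neither is stated for 4.4.2.2, and the synopsis limit to chemotherapy could apply to both. The end date is unspecified; a contradiction is not shown.
- **A reader might infer a definite bias against trilaciclib.** That needs a count response and longer trilaciclib treatment. The offsets suggest a count: cycles with an event go with log(cycles), and for separately dated antibiotic and infection events in 4.4.3.3 "the offset variable in the modified Poisson regression model will be the log transformed duration of treatment (weeks) rather than the number of cycles". But 4.4.2.2 also defines a yes/no variable and does not name the response.
- **A reader might infer that the other offsets are wrong as well.** For count responses they match their counting units. The Week 5 problem belongs to the transfusion endpoint.

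**Conclusion.** The mismatch is real and rests on two adjoining statements in SAP 4.4.2.2. With a count response, the adjusted rate ratio has no bias if arms are treated equally long, and is about 1.01–1.10 under no true difference at assumed means of 4.2–5 v 4 cycles. It works against trilaciclib if trilaciclib is given longer and in its favour if it is given for a shorter time. For a yes/no response the direction is not established. The weekly-rate shortfall of 28–33% needs no difference between arms, but applies to the MAHE transfusion component only if that rate divides by the same treatment weeks.

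Severity is minor. The shift is small beside the interval, and the CMH comparison, the Cycle 1 DSN analysis and the sample size are unaffected. Confidence is high in the mismatch itself. The size depends on the assumed treatment lengths, the constant rate from Week 5 and the end date chosen.

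**What to change.** In SAP 4.4.2.2:

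1. Model the number of transfusions on or after Week 5, with offset log(weeks from the start of Week 5 to the date on which the count ends).
2. State that end date and use it for both count and offset. Set it consistently with the synopsis limit to the chemotherapy period and the cycle-end rule in 4.1, and cut it at death, end of study or last contact. 4.4.2.4 has similar wording for time to first MAHE, which is "censored at the end date of the last cycle, date of death, end of study, or last contact date".
3. Use the same denominator for the transfusion component's weekly rate in 4.4.2.4.
4. Report, per arm, the patients with no time from Week 5, and keep the offset-free CMH comparison on the full FAS.

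**Cost.** This takes SAP wording and one model statement, with no new data. Patients with no time from Week 5 leave this one model.

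- With the Day 1 + 36 end, a one-cycle patient keeps 36/7 − 4 = 1.14 weeks, so only those who die, withdraw or are lost before Week 5 leave.
- With a 21-day end, one-cycle patients leave too. At 5 v 4 cycles this is about 1–13% on placebo and 0–4% on trilaciclib if everyone is capped at 6 cycles.
- The cap applies only to first-line patients. If half the patients are on uncapped topotecan with geometric cycle counts (an assumption), one-cycle shares in that half are 1/4 and 1/5. The losses become about 13–19% (12.5% plus half of 1–13%) and 10–12% (10% plus half of 0–4%).

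The end date therefore decides how much of the FAS this model keeps. If trilaciclib is given longer, the corrected count ratio moves slightly in its favour, so the change should be fixed before unblinding.

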4.4.2.3. Use rate of granulocyte colony-stimulating factor

Prophylactic use of any prophylactic colony-stimulating factors (including granulocyte colony-stimulating factor G-CSF, granulocyte-giant cell colony-stimulating factor, erythropoietin) is not permitted in principle in Cycle 1, but febrile neutropenia with high-risk infections or risk factors suggestive of poor prognosis is permitted for therapeutic use.

Determine if G-CSF is used in this cycle by comparing the start and end dates of each use of granulocyte colony-stimulating factor (G-CSF) with the start and end dates of the treatment cycle. If the date of G-CSF use lies between the start and end dates of the cycle, the cycle will be considered as having G-CSF use. The total number of events with G-CSF use is the total number of cycles with at least one GCSF administration. If a patient does not take any G-CSF, the number of G-CSF administration events for that patient is zero. Thus, whether a patient experiences an event of G-CSF administration is defined as a binary variable (yes or no); "yes" if the number of cycles with G-CSF administration is ≥ 1 and "no" otherwise.

Statistical analysis method is similar to that for SN incidence described in Section 4.4.2.1.

4.4.2.4. Total occurrence of major adverse hematologic event

Major adverse hematologic event (MAHEs) are composite endpoints to assess the effect of Trilaciclib. MAHE consists of the following 5 component events:

- Involved hospitalization
- Leading to chemotherapy dose reduction
- Febrile neutropenia
- Extended SN (greater than 5 days)
- RBC transfusion occured on/after Week 5.

The total number of events for each MAHE component is the sum of the number of events that occurred on the date of first study drug administration and before the end of the last treatment cycle. The total number of events for MAHEs during treatment is the sum of the number of events for each MAHE component. For patients who does not experience any MAHE, the total number of MAHE events is 0.

MAHEs will be coded using the most current version of MedDRA and the total number of MAHEs, duration of treatment (weeks), weekly event rates, and cumulative event rates every 3 weeks will be summarized by number of lines of treatment. According to the actual MAHEs, the above summaries will be repeated separately by component events , but for MAHE component events leading to chemotherapy dose reduction and SN prolongation, the cumulative

event rates will be summarized by cycle rather than every 3 weeks. Part 2 of the study will also analyze the adjusted rate ratio between the Trilaciclib and placebo groups using a negative binomial regression model. The model includes the three IRT-based randomization stratification factors and treatment group as fixed effects, and the log-transformed values of treatment duration (weeks) or cycle number as offset variables. Two-sided P values, aRR (Trilaciclib versus placebo) and their 95% CIs will be provided. Cumulative incidence of MAHEs within specified subgroups will be presented using forest plots.

Time to first onset (months) for each MAHE component event = (date of first MAHE component event – date of first study drug administration + 1)/30.

For patients who developes MAHEs, the time (months) from the first study drug administration (randomization date in Part II) to the first occurrence of MAHEs will be summarized and Kaplan-Meier curves will be provided. Time to first MAHE refers to the event with the shortest time to first occurrence of the MAHE component; if a patient does not have an MAHE, it will be censored at the end date of the last cycle, date of death, end of study, or last contact date for that patient, whichever cames first.

Kaplan-Meier methods will be used to estimate 25%, median, and 75% time (months) to first MAHE and provide 95% CIs (months). Part 2 of the study calculates the HR and its 95% CI between the two treatments (Trilaciclib versus placebo) from a stratified Cox proportional hazards model with treatment group and IRT-based randomization stratification factors as fixed effects, and 2-sided P values will be calculated from a stratified log-rank test.

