4.4.1.1. Strategy 1: Missing ANC values not imputed

For patients who experienced at least 1 episode of severe neutropenia (SN) within each cycle, a DSN is defined as the number of days from the date of the first absolute neutrophil count (ANC) value $< 0.5 \times 10^{9}$ /L in that cycle to the date of the first ANC value $\ge 0.5 \times 10^{9}$ /L that met the following requirements: (1) occurred after an ANC value $< 0.5 \times 10^{9}$ /L, and (2) no other ANC value $< 0.5 \times 10^{9}$ /L occurred between that date and the end of that cycle (otherwise the SN event is considered not resolved at the end of that cycle). If a patient does not experience any SN during the cycle, DSN will be counted as 0 for that cycle. Exceptions will be handled using the following rules:

- If the SN event is not resolved at the end of the cycle, the DSN will be calculated as above, but the end date is the end date of the cycle;
- If a patient dies during the period of the SN event, the DSN will be calculated as described above, but the end date is the date of death;
- If a patient withdraws consent or is lost to follow-up during the period of the SN event, the DSN will be calculated as described above, but the end date will be the last ANC assessment date before the end of the study.

Nonparametric analysis of covariance (Nonparametric ANCOVA) will be used to evaluate DSN-based differences in efficacy between the test and placebo groups. The nonparametric covariance model will include covariates of baseline ANC study value as a continuous variable, and fixed effects of number of lines of treatment (1st line versus 2nd/3rd line), ECOG (0 or 1 versus 2), brain metastases (yes versus no), and treatment arm (Trilaciclib versus placebo) as categorical variables. Stratification will be combined or reduced appropriately if the number of patients within a stratum is small. The p-value for the 2-sided test will be calculated from the model, and it will be provided the difference in means between the two treatment groups and its 95% confidence interval (CI) based on Satterthwaite t-test, as well as the median difference between the groups and its 95% confidence interval estimated using Hodges-Lehmann.

In addition, DSN will be summarized for each cycle by treatment group using descriptive statistics.

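### MAHE is the only key secondary endpoint modelled without a baseline blood count; the model is valid but may give away some precision, and the SAP gives no reason

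*SAP*

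**What the plan says.** SAP 4.4.2 names four key secondary endpoints: SN, RBC transfusion on or after Week 5, G-CSF use and MAHE. Their models use these baseline counts:

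- **SN (SAP 4.4.2.1):** modified Poisson regression. "The model includes baseline ANC measurement as covariate and IRT-based randomization stratification factors".
- **RBC transfusion (SAP 4.4.2.2):** the SN method, "except hemoglobin (HGB) baseline measurement will be used as covariate instead of" baseline ANC.
- **G-CSF use (SAP 4.4.2.3):** "Statistical analysis method is similar to that for SN incidence described in Section 4.4.2.1", so baseline ANC by cross-reference.
- **MAHE (SAP 4.4.2.4):** the plan is to "analyze the adjusted rate ratio between the Trilaciclib and placebo groups using a negative binomial regression model". On its terms: "The model includes the three IRT-based randomization stratification factors and treatment group as fixed effects". There is also an offset for treatment weeks or cycles, but no baseline count. The Cox model for time to first MAHE has none either.

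The primary analysis of Cycle 1 DSN (SAP 4.4.1.1) also uses "covariates of baseline ANC study value as a continuous variable".

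One part of the SAP goes the other way. For the remaining binary endpoints (SAP 4.4.3.3), which include febrile neutropenia, the SN method applies "except that baseline ANC measurements will not be included as covariates in the modified Poisson regression model".

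**The concern.** MAHE sums five kinds of event. Two come from outcomes that the SAP adjusts for when it analyses them alone. SN lasting more than 5 days is a duration threshold on the ANC-adjusted outcome, and RBC transfusion on or after Week 5 is the haemoglobin-adjusted endpoint itself. The adjustment disappears once these events are added into the composite.

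Both counts are available before treatment. The flow sheets (SAP Appendix 2, haematology footnotes) require haematology within 24 hours before the first dose in both the EC and the topotecan cohorts.

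At stake is the width of the confidence interval for the MAHE rate ratio, and how far chance imbalance in baseline counts stays in the estimate. Stratifying by line of therapy, ECOG and brain metastases does not balance those counts directly. The trial was sized for DSN alone, and neither document states power or precision for MAHE.

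**Working it through.** **1. The plan's own figure.** SAP 2.2 gives about 95% power for DSN with 35 per group. The Poisson means are -ln(0.90) = 0.105 and -ln(0.55) = 0.598. Over 10,000 simulated trials with a two-sided Mann-Whitney-Wilcoxon test at 0.05, power is 0.944, which agrees. For dropout, 70/(1 - 0.12) = 79.5, rounded up to 80. These figures concern DSN and give no input for MAHE.

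**2. Assumed MAHE inputs (none are in the documents).** Placebo mean 0.5 to 2 events per patient, dispersion k of 0.5 to 2, rate ratio 0.5, 40 per arm. R is the share of between-patient variance that the two counts explain.

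**3. Large-sample formula.** With μ the mean event count in an arm,

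Var(log RR) = Σ over arms of [1/μ + k(1 - R)] / 40.

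- Placebo mean 1, k = 1, R = 0: (1 + 1)/40 + (2 + 1)/40 = 0.125, SE 0.354.
- Same with R = 30%: (1 + 0.7)/40 + (2 + 0.7)/40 = 0.110, SE 0.332, ratio 0.94.
- Most favourable case (mean 2, k = 2, R = 30%): variance falls from 0.1375 to 0.1075, ratio 0.88.
- Least favourable case (mean 0.5, k = 0.5, R = 30%): variance falls from 0.1750 to 0.1675, ratio 0.98.
- At R = 10% the ratio lies between 0.96 and 0.99 over the whole grid.

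This formula charges nothing for estimating two more coefficients, so it flatters adjustment in a trial of 80.

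**4. Simulation at 80 patients.** Three binary stratification factors were in both models. The entries are the empirical SD of the log rate ratio with the counts divided by the SD without them.

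| R | mean 1, k = 1 | mean 2, k = 1.5 |
|---|---|---|
| 0 | 1.01 | 1.02 |
| 5% | 1.02 | not run |
| 10% | 1.01 | 0.98 |
| 20% | 0.99 | not run |
| 30% | 0.96 | 0.94 |
| 50% | 0.93 | not run |

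Power at R = 30% moved from 0.55 to 0.59 in the first setting and from 0.65 to 0.70 in the second. There were 600 and 400 trials per setting. Fits that failed or gave extreme estimates were excluded.

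**5. The same question as effect per SD.** Two further simulations used 1,000 trials per setting, with two and with three stratification factors. The first assumed placebo mean 1.0 to 1.5, dispersion 0.5 to 1.0 and rate ratio 0.5; the prevalences of the factors in the second were also assumed.

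| Log-rate effect per SD, each count | Two factors | Three factors |
|---|---|---|
| 0 | SD up 1 to 3%; power 0 to -2 points | SE up about 2% (bootstrap interval 0.7 to 3.7%) |
| 0.2 | SD from +2.5% to -3%; power within about 1.5 points | SE -1% to +1% |
| 0.35 | SD down 4 to 8%; power up 3 to 6 points | SE down 5 to 7% |

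**6. Cross-check by formula.** Two independent counts at 0.35 add 2 × 0.35² = 0.245 to the between-patient variance, on top of a residual k.

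- Mean 1, residual k = 1: √[(1 + 2 + 2 × 1) / (1 + 2 + 2 × 1.245)] = √(5/5.49) = 0.954.
- Mean 1.5, residual k = 0.5: √(3/3.49) = 0.927.

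The predicted fall of 5 to 7% matches the simulations. At 0.2 the added variance is 0.08, and the ratios are √(5/5.16) = 0.984 and √(3/3.16) = 0.974. That gain of 2 to 3% is about what the two extra coefficients cost.

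**7. How strong 0.35 is.** A patient at +1 SD has exp(0.70) = 2.0 times the event rate of one at -1 SD, for each count. Together the counts explain about 0.245/1.245 = 20% to 0.245/0.745 = 33% of between-patient variance.

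**The case against.** The strongest case is that this is a choice, not a slip. SAP 4.4.3.3 deliberately drops baseline ANC for febrile neutropenia, itself a MAHE component, and for Grade 3/4 haematologic toxicity. The SAP can be read as giving each single-lineage endpoint its matching count and giving none to composite or clinical-event endpoints. No model in the SAP uses both counts. This reading is possible, but the SAP does not state it. The endpoints in 4.4.3.3 are lower-tier, so MAHE still stands alone among the key secondaries.

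The link between baseline counts and MAHE may also be weak. Protocol 2.2 counts hospitalization and chemotherapy dose reduction from any cause. Protocol 4.1 requires ANC of at least 1.5 × 10⁹/L and haemoglobin of at least 90 g/L, which may narrow the baseline range. Line of therapy, already in the model, may carry some of the same information. All this stands and limits the likely gain.

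The stakes are also modest. Neither document gives the key secondary endpoints a testing hierarchy or allocated alpha, so a power gain concerns a test without a confirmatory role. Protocol 7.1 rests the multilineage assessment on the secondary endpoints together, not on MAHE alone. This stands too.

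A reader might infer that baseline ANC and haemoglobin are established predictors of MAHE, so that precision is certainly lost, or that the MAHE estimate is biased. The documents support neither. They report no association of these counts with MAHE, and using a covariate in another model does not show one. Randomization with adjustment for the stratification factors makes the existing estimate valid, and type I error is not affected.

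**Conclusion.** The inconsistency is established: MAHE alone among the key secondary endpoints has no baseline count in its model, two of its components come from outcomes that are adjusted elsewhere, and no reason is stated. Confidence in that is high.

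The loss of precision is possible but not shown. The likely range for the SE runs from about 3% wider to about 8% narrower, depending on how prognostic the counts are. A gain near the upper end needs each count to double the event rate over 2 SD, and nothing in the documents supports that strength. The large-sample best case of 12% also needs a high event rate and strong overdispersion. Confidence in the size of the gain is therefore moderate to low.

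The change is still worth making. The possible loss is small and bounded, the possible gain is somewhat larger, and with a log link under randomization the rate ratio being estimated stays essentially the same.

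**What to change.** In SAP 4.4.2.4, add baseline ANC and baseline haemoglobin to the MAHE negative binomial model, alongside the stratification factors, treatment and offset. Both should be continuous and taken as the last valid value before the first dose, which is the study baseline already defined in SAP 4.1. Report the model without them as a sensitivity analysis.

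The change must be fixed before MAHE data are unblinded, because covariates chosen later would look data-driven. SAP 4.7 unblinds some sponsor staff at the primary analysis after Cycle 1 and lets other applicable secondary endpoints be analysed then, so the safe deadline is before that analysis.

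The cost is one SAP sentence and two variables that are already collected. The statistical downside is an SE up to about 3% wider if neither count is prognostic.
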